4.2. Definitions

- I. Enrolled: From time consented to participate until designated as a screen failure or have either been discontinued from the study or completed it.
- II. Randomized: when a randomization number is assigned
- III. Screen Failures: signed informed consent, but then determined to be ineligible or withdraws before being randomized
- IV. Discontinued: randomized, but then withdrawn by investigator or withdraws consent
- V. Completed: Subjects are considered completed when they are followed through to day 28 or died before that.

4.3. Study population

4.3.1. Inclusion Criteria for Enrollment

1. Subjects must be 18 years of age or older
2. Close contact exposure (as defined by CDC guidelines) to person with COVID-19 within 96 hours of randomization (and 120 hours of receipt of plasma)

4.3.2. Exclusion Criteria for Enrollment

1. Medical, psychiatric, or cognitive illness or recreational drug/alcohol use that in the opinion of the principal investigator, would affect subject safety and/or compliance
2. Symptoms consistent with COVID-19 infection at time of screening (sudden onset of at least one of the following: fever, cough, shortness of breath)
3. Laboratory evidence of COVID-19 infection at time of screening
4. History or known laboratory evidence of previous COVID-19 infection
5. A history of or known prior allergic reaction to transfusion blood product
6. Receipt of SARS-CoV-2 Vaccine

Table: Schedule of Events

Study period	Screen	Baseline	Transfusion	Follow up						
				1	3	7	14	28	60	90
Day	-1 to 0	0	0							
Window				+/- 1 day	+/- 1 day	+/- 1 day	+/- 3 days	+/- 3 days	+/- 3 days	+/- 8 days
Eligibility										
Informed consent	x									
Demographic and Medical history	x									
COVID-19 symptom survey	x									
SARS-CoV-2 molecular testing for eligibility	x									
Pregnancy test ⁴	x									
ABO ⁵	x									
Study Drug Administration										
Randomization		x								
Drug infusion			x							
Study Procedures										
Vital signs	x	x	xxxx ⁶	x		x	x			
Physical examination			x							
COVID-19 symptom screen	x	x	x	x	x	x	x	x	x	
Concomitant medications	x	x	x							
Assessment of clinical event scale of disease severity ⁷		x		x	x	x	x	x	x	
Adverse event monitoring		x	x	x	x	x	x	x	x	

⁴ Result of urine or serum pregnancy test for women of childbearing potential must be documented prior to transfusion

⁵ Assessment of ABO type on file or determination of ABO type if not on file

⁶ Vital sign testing: Immediately prior to infusion, 10-20 minutes after start of infusion, at completion of infusion and 30-60 minutes after the end of the infusion

⁷ Assessment evaluates whether subject has shifted from “no clinical or laboratory evidence of COVID-19 infection to any of the clinical event scale of disease severity

Laboratory testing										
CBC and CMP	x			x		x	x			
SARS-CoV-2 molecular testing ⁸	x			x		x	x	x		
Blood for future testing ⁹	x			x		x	x			x

4.3.3. Subject Withdrawal

- I. Subjects can terminate study participation and/or withdraw consent at any time without prejudice.
- II. Randomized subjects who withdraw from the study will not be replaced.
- III. The investigator may withdraw subjects if they are lost to follow up, non-compliant with study procedures or if the investigator determines that continued participation in the study would be harmful to the subject or the integrity of the study data
- IV. Discontinuation of the study: The study sponsor, FDA and IRB all have the right to terminate this study at any time

4.3.4. Intervention

- I. Subjects will be randomized in a 1:1 ratio to receive treatment vs SARS-CoV-2 non-immune plasma
- II. Study drug: The investigational product is anti-SARS-CoV-2 convalescent plasma. Patients identified as having recovered from COVID-19 will serve as potential donors. Donors with SARS-CoV-2 antibody titers $\geq 1:320$ by validated ELISA will be used for the trial. The ELISA testing will be performed in a CLIA certified laboratory. Potential donors and samples will be screened for transfusion-transmitted infections (e.g. HIV, HBV, HCV, WNV, HTLV-I/II, *T. cruzi*, ZIKV) and plasma will be collected using apheresis technology. This is similar to standard blood bank protocols.
- III. Samples of convalescent plasma will be reserved by the blood bank for further testing
- IV. Active arm will receive 1 unit of anti-SARS-CoV-2 plasma with titers $\geq 1:320$)
- V. Control arm will receive 1 unit of SARS-CoV-2 non-immune plasma
- VI. Both active and control drugs will be in standard plasma unit bags, with a study-specific ISBT label.
- VII. For blood that will be collected locally (Johns Hopkins) the source of donor plasma will be as detailed in protocol JHM IRB00248402.
- VIII. all subjects must be negative for active SARS-CoV-2 via a validated molecular test within 24 hours preceding the plasma infusion.

⁸ Sites could include nasopharyngeal, throat

⁹ Includes anti-SARS CoV-2 titers.

4.3.5. Randomization

- I. Subjects enrolled in the study will be randomized using an interactive web response system (IWRS) to receive study drug vs control at a 1:1 ratio.
- II. Randomization will occur after the result of the initial coronavirus testing is known to be negative.

4.4. Rationale for dosing

Dose calculation is based on 1 unit (minimum of 175 mL) of plasma with anti-SARS-CoV-19 titers of >1:320 and 1 unit of standard plasma. For the purposes of the proposed trial, we will require titers \geq 1:320. The current FDA recommendations target titers that are optimally greater than 1:320 in the event that testing is available. We have favored a more conservative \geq 1:320 given findings from a pilot study in China that showed most (39/40) convalescent donors had titers \geq 1:160 (Duan K, et al.medRxiv. 2020:2020.03.16.20036145). We intend to infuse a minimum of 175 ml (1 unit) of plasma to all individuals.

4.5. Study drug administration

- Drug will be administered within 24 hours of randomization
- Transfusions for Johns Hopkins site participants will be performed at HEIC and Blood Bank approved JHM locations such as: 1) The Adult Clinical Research Unit (CRU) on Blalock 3 at Johns Hopkins Hospital and 2) the Neurosciences Consultation and Infusion Center at [name].
- If infusion takes place at the Adult CRU, Adult CRU registered nurses (RN's) will administer the infusion per JH policy. They will attend to the participant throughout the infusion and post infusion observation period. For infusion at any HEIC approved JHM location, registered nurses (RN's) from Johns Hopkins will administer the infusion per JH policy. They will attend to the participant throughout the infusion and post infusion observation period. All RNs are BLS trained. A study physician or advanced practice clinician with clinical privileges at JH will be available by phone and within 5 minutes physical response time to respond to any emerging event during the infusion.
- For non-Johns Hopkins sites, infusion will take place in the area designated for this research project. All infusions will be performed and monitored by appropriate personnel as defined by institutional policy for blood product transfusion.
- Infusion rate \leq 500 mL/hour
- Vital signs will be taken immediately prior to infusion, 10-20 minutes after start of infusion, at completion of infusion, and 30-60 minutes after the end of the infusion.

- Medicines for transfusion reactions (e.g. acetaminophen, diphenhydramine) may be given.
- If an AE develops during infusion, the infusion may be slowed or stopped as per investigator or infusion monitor decision.
 - Management of transfusion-associated AE will follow AABB guidelines; Outside of a simple allergic transfusion reaction, the transfusion will be discontinued and investigated appropriately (i.e. per standard practice guidelines).
- Following completion of the infusion, the participant will remain in the infusion area under observation for 30-60 minutes. If after that time the participant is not experiencing any adverse events, they may be discharged home. A written post-infusion information sheet will be given to the participant prior to discharge. The sheet will list risk and possible complications of blood transfusion. Depending on the severity and nature of the complication, the participant is advised to contact their healthcare provider or call 911.

4.5.1. Concomitant medications will be documented on the CRF

- Prescription medications
- Blood products

4.5.2. Prohibited Medications: Any approved or investigational drug with established activity against SARS-CoV-2 (Unless subject becomes ill with COVID-19 and qualifies for treatment)

5. STATISTICAL CONSIDERATIONS

5.1. Sample Size and Power Considerations

The planned sample size for the trial is 500 subjects, randomized in a 1:1 ratio to convalescent titer anti-SARS CoV-2 plasma vs SARS-CoV-2 non-immune plasma.

To evaluate the power of the study, the following assumptions were made:

- a. The primary analysis will compare efficacy/prevention in the convalescent titer and SARS-CoV-2 non-immune plasmas groups using proportional odds model and a one-sided Type I error rate (alpha) of 0.05 (i.e., for superiority) and Type II error rate (beta) of 0.2
- b. It is anticipated that very few of these subjects will be randomized and not start study plasma infusion (and so be excluded from the primary analysis) or be lost to follow-up prior to Day 28 (and so have missing data for the primary endpoint).

- c. 13% incidence of symptomatic disease in exposed individuals treated with SARS-CoV-2 non-immune plasma
- d. 6.5% incidence of symptomatic disease in exposed individuals treated with anti-SARS CoV-2 plasma

We estimate a sample size of 488 patients (244 in each arm) would be sufficient to detect a difference in outcomes between those two arms with a power of 0.8. To allow for some loss-to-followup, we have rounded our target sample to 500 patients.

5.2. Statistical Analysis

Primary endpoint:

Our primary hypothesis is that by providing anti-SARS-CoV-2 plasma, the cumulative incidence of the development of COVID-19 will be lower among the individuals receiving HCIP as compared to those receiving control plasma over the course of follow-up. Therefore, our primary endpoint is the development of COVID-19 regardless of severity.

Our analysis will be a time to event analysis examining the effect of anti-SARS-CoV-2 plasma. We will estimate the survival function for each treatment arm in order to estimate the risk difference over time as well as the restricted mean survival time which is the area under the survival function and provides the expected mean time to hospitalization or death up to time t^{22} . Our approach will be to estimate the cumulative incidence using the doubly robust estimator based upon targeted minimum loss based estimator as described by Diaz et al [Díaz, I., Colantuoni, E., Hanley, D.F. *et al.* Improved precision in the analysis of randomized trials with survival outcomes, without assuming proportional hazards. *Lifetime Data Anal* **25**, 439–468 (2019)]. By adjusting for baseline covariates that are related to the outcome, we increase precision. The TMLE based approach was shown to increase precision by around 10% to 20% over an inverse probability weighted or augmented inverse probability weighted estimator. As stated above, we will use a hybrid approach of adjusting for pre-specified variables (age) and an algorithmic approach to identify additional variables related to the outcome. Specifically, a random survival forest will be used to identify variables that are related to the outcome in order to increase precision. We will use a random survival forest blinded to the treatment arm allocation and *not* including an indicator variable for treatment. The following pre-randomization variables will be considered: clinical site, race, ethnicity, sex, category of exposure, hematology factors and other laboratory markers (i.e., CBC and metabolic panels), body mass index, ABO blood group, targeted physical exam, and prior comorbidities that have specifically been associated with worse COVID-19 outcomes including: asthma, chronic kidney disease, chronic lung disease (COPD, idiopathic pulmonary fibrosis, cystic fibrosis), diabetes, hemoglobin disorders (thalassemia, sickle cell disease), immunocompromised (cancer, HIV, organ transplantation, prolonged use of corticosteroids), chronic liver disease,

hypertension, and serious heart conditions (heart failure, coronary artery disease, cardiomyopathies, pulmonary hypertension) [Guan W-j, Liang W-h, Zhao Y, et al. Comorbidity and its impact on 1590 patients with COVID-19 in China: a nationwide analysis. *Eur Respir J* 2020; 55: 2000547, <https://www.cdc.gov/coronavirus/2019-ncov/need-extra-precautions/groups-at-higher-risk.html>].

The primary outcome analysis will be the adjusted comparison of proportions of cumulative incidence of SARS-CoV-2 infection (symptoms compatible with infection and RT-PCR positive) at day 28 comparing the risk-difference and restricted mean survival time between treatment groups with a significance threshold of $p=0.047$ (p -value adjusted for interim analysis) for a one-sided test.

Finally, statistical inference will use a one-sided Type 1 error rate of 0.05 for superiority and 95% confidence intervals (note: interim analyses are based upon O’Brian-Flemming spending function see below under section 8.3 Halting Criteria for Study).

5.2.1. Analysis of AE data

Analysis of AE data will primarily be descriptive based on MedDRA coding of events. The proportion of subjects experiencing an SAE and the proportion experiencing a Grade 3 or higher. AE will be compared between randomized arms using Fisher’s Exact Test.

5.2.2. Analysis of disease severity

A secondary hypothesis is that individuals receiving anti-SARS-CoV-2 convalescent plasma are likely to have less disease severity than control. Therefore, this analysis is restricted to individuals who have developed a SARS-CoV-2 infection. We have devised a clinical event scale for disease severity based on the COVID clinical severity scale which is composed of clinical events that range from being symptomatic and not hospitalized, to being hospitalized, to mechanical ventilation/ICU, to death.

We will separately analyze each of the clinical events by determining the cumulative incidence from time from randomization. Similarly to the primary analysis, we will utilize the TMLE based estimator and adjust for age and any pre-specified candidate variables selected via the algorithm as described above. If individuals jump in severity (e.g., progress from symptomatic not hospitalized to ICU without being hospitalized in non-ICU) then we will interval censor the lower events between the two time points prior to more severe and time of severe clinical event. This will allow individuals to contribute to the progression through the clinical events.

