4. INVESTIGATIONAL PLAN

4.1. Study Objectives

4.1.1. Primary Efficacy Objective: Evaluate at day 28, the efficacy of treatment with high-titer Anti- SARS-CoV-2 plasma versus control (SARS-CoV-2 non-immune plasma) in subjects exposed to COVID-19

4.1.2. Primary Safety Objective: Evaluate the safety of treatment with high-titer Anti-SARS-CoV-2 plasma versus control (SARS-CoV-2 non-immune plasma) in subjects exposed to COVID-19

4.1.3. Secondary Objectives:

- I. Cumulative incidence of disease severity between the anti-SARS-CoV-2 convalescent plasma and control groups after individuals develop SARS-CoV-2 infection. Severity of disease will be measured using a clinical event scale of disease severity (evaluated up to Day 28):
 1. Death
 2. Requiring mechanical ventilation and/or in ICU
 3. non-ICU hospitalization, requiring supplemental oxygen;
 4. non-ICU hospitalization, not requiring supplemental oxygen;
 5. Not hospitalized, but with clinical and laboratory evidence³ of COVID-19 infection

4.1.4. Other Objectives:

³ Validated test for presence of SARS-CoV-2

- I. Compare the anti-SARS-CoV-2 convalescent plasma and control (SARS-CoV-2 non-immune plasma) groups for anti-SARS-CoV-2 titers at days -1 to 0, 1, 7, 14 and 90
- II. Compare the rates and duration of SARS-CoV-2 molecular testing positivity amongst the anti-SARS-CoV-2 convalescent plasma and control (SARS-CoV-2 non-immune plasma) groups at days 1, 7, 14 and 28
- III. Compare the levels of SARS-CoV-2 RNA amongst the anti-SARS-CoV-2 convalescent plasma and control (SARS-CoV-2 non-immune plasma) groups at days -1 to 0, 1, 7, 14 and 28
- IV. Understand how the immune system responds to COVID-19 infections and try to understand why some people have mild symptoms and other people have life-threatening disease.

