5.3. Endpoints

Primary Efficacy Endpoint:

28 day incidence of COVID-19 infection with both clinical and laboratory evidence.

Primary Safety Endpoints:

1. Cumulative incidence of serious adverse events categorized separately as either severe infusion reactions and ARDS during the study period
2. Cumulative incidence of grade 3 and 4 adverse events during the study period

Secondary Endpoints

1. 28 day incidence of severe COVID-19 infection defined by death or initiation of mechanical ventilation.
2. Anti-SARS-CoV-2 titers at days -1 to 0, 1, 7, 14, and 90.
3. Rates and duration of SARS-CoV-2 molecular testing positivity at days 1, 7, 14, and 28.

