## Study Design

CSSC-001 is a two-arm, parallel-group, multi-center, randomized superiority trial in which outpatient adults with recent exposure to SARS-CoV-2 but no current infection will be randomized to receive either human coronavirus immune plasma (HCIP) or control (SARS-CoV-2 non-immune) plasma. This randomized, double-blind, controlled, phase 2 trial will assess the efficacy and safety of HCIP to reduce the cumulative incidence of the development of COVID-19 during study follow-up. Adults 18 years of age or older, with high risk exposure (see below for definition) to person with COVID-19 within 96 hours of enrollment (and 120 hours of receipt of plasma). A total of approximately 500 eligible subjects will be randomized in a 1:1 ratio to either HCIP or control plasma.

**High risk exposure will be defined** as currently defined by CDC and modified as the CDC makes changes. Currently this includes any close contact exposure (as defined by CDC guidelines) to person with COVID-19. Health Care Personnel (HCP) are defined as physicians, nurses, nursing assistants, therapists, technicians, emergency medical service personnel, dental personnel, pharmacists, laboratory personnel, autopsy

personnel, students, trainees and contractual staff. Persons not directly involved in patient care such as clerical, dietary, housekeeping, laundry, security, maintenance, billing, and volunteers, but who are potentially exposed to SARS-CoV-2 in the healthcare setting, also fall under the category of HCP in this protocol.

*Primary Outcome:*

- The primary outcome of CSSC-001 will be the cumulative incidence by day 28 of the development of COVID-19 (symptoms compatible with infection and/or RT-PCR positive) regardless of disease severity comparing those randomized to HCIP to those who are transfused with control plasma.

*Secondary Outcome:*

- Compare the cumulative incidence of disease severity between those randomized to HCIP and control plasma. Severity of disease will be measured using a clinical event scale of disease severity evaluated up to Day 28:
  1. Death
  2. Requiring mechanical ventilation and/or in ICU
  3. non-ICU hospitalization, requiring supplemental oxygen;
  4. non-ICU hospitalization, not requiring supplemental oxygen, or a stay of >24 hours for observation in an ED, field hospital, or other healthcare unit\*, or any receipt of O2 for >24 hours, outside of hospital\*

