## Secondary Analyses:

A secondary hypothesis is that individuals receiving anti-SARS-CoV-2 convalescent plasma are likely to have less disease severity than control. We have devised a clinical event scale for disease severity based on the COVID clinical severity scale which is composed of clinical events that range from being not infected to death. The event scale is as follows:

1. Death
2. Requiring mechanical ventilation and/or in ICU
3. non-ICU hospitalization, requiring supplemental oxygen;
4. non-ICU hospitalization, not requiring supplemental oxygen  
or  
a stay of >24 hours for observation in an ED, field hospital, or other healthcare unit\*  
or  
any receipt of O2 for >24 hours, outside of hospital\*
5. Not hospitalized, but with clinical and laboratory evidence of COVID-19 infection (symptomatic infection)

---

 Positive molecular testing for SARS-CoV-2

\*with surge of infections in December 2020 and hospitals becoming more full, these two were put into the clinical events scale as hospitalization equivalents

6. Not hospitalized, no clinical symptoms compatible with COVID-19, but with laboratory evidence of COVID-19 infection (asymptomatic infection)
7. No symptoms compatible with infection, no laboratory evidence of COVID-19 (No indication of infection)

This analysis will be done using the status of participants by day 32 (corresponding to day 28 visit allowing for window around the scheduled visit) using a doubly robust estimators for ordinal outcomes and adjusted for the pre-specified candidate variables selected via the algorithm as described above. The doubly robust estimator that will be used is that as outlined by Benkeser et al. (2020) based upon a non-parametric extension of the log-odds ratio by Diaz et al. (2016). A sensitivity analysis will be done in which participants who have indication of positive infection (e.g. clinical scale event <7) at  $\leq 3$  days after transfusion.

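### Protocol 5.2.2 limits the severity comparison to infected participants, a group formed after randomisation, and so conflicts with the SAP and with the protocol's own endpoints

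*Protocol*

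**What the plan says.** Protocol 5.2.2 starts from a hypothesis about everyone who receives convalescent plasma, then narrows the analysis: "Therefore, this analysis is restricted to individuals who have developed a SARS-CoV-2 infection". The secondary objective, worded alike in Protocol sections 1 and 4.1.3, compares severity "after individuals develop SARS-CoV-2 infection".

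Other parts of the plan describe a different comparison:

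- **Protocol 5.2.2, time origin:** "We will separately analyze each of the clinical events by determining the cumulative incidence from time from randomization".
- **Protocol 5.3, first secondary endpoint:** "28 day incidence of severe COVID-19 infection defined by death or initiation of mechanical ventilation", with no restriction to the infected.
- **SAP, Study Design:** "Compare the cumulative incidence of disease severity between those randomized to HCIP and control plasma", on a seven-level scale whose last level is no indication of infection.
- **SAP, Power and Sample Size:** modified ITT for all analyses, excluding only randomised participants who do not start the infusion.
- **SAP, Secondary Analyses:** "This analysis will be done using the status of participants by day 32", with one doubly robust ordinal estimator in place of event-by-event cumulative incidence.

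The scales differ too. Protocol 4.1.3 and 6.1 have five levels. Protocol section 1 has seven, two of them hospitalisation equivalents. The SAP has a different seven: it folds those equivalents into level 4 and adds asymptomatic infection and no infection.

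**The concern.** Infection is the primary outcome, and the design assumes that plasma halves its symptomatic form. If that is right, the infected HCIP participants are those in whom plasma failed, while the infected controls were not filtered in this way. A severity difference between these groups mixes the effect of plasma on severity with the selection of who became infected. Baseline adjustment, as planned with TMLE, removes this only if every common cause of infection and of severity is measured.

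The stated secondary hypothesis therefore has two analyses on file, with different populations, scales and estimators. They can point in different directions, and the texts do not say which governs.

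**Working it through.** **Inputs.** From Protocol 5.1: 13% control and 6.5% HCIP incidence of symptomatic disease, 1:1 allocation, 500 in total (250 per arm). The severe share q among infected controls is not in the documents; q = 10%, 20% and 30% are assumptions.

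**The plan's own figure.** Neither document gives a sample size or power for the severity analysis. The primary sample size can be approximately reproduced. Under the SAP's exponential model, HR = ln(1 − 0.065)/ln(1 − 0.13) = 0.4826. Schoenfeld's formula at one-sided 0.05 and 80% power gives 47 events. With a mean event probability of (0.13 + 0.065)/2 = 0.0975, 47/0.0975 = 482, which is 1.2% below the stated 488.

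**Size of the restricted set.** 250 × 0.13 = 32.5 control cases and 250 × 0.065 = 16.25 HCIP cases, about 49 of 500.

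**Scenario A: plasma prevents only mild cases.** Severe cases in each arm = 32.5 × q. The severe share among infected HCIP participants = 32.5q/16.25 = 2q.

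| q (assumed) | Severe cases per arm | Severe risk per randomised participant, each arm | Infected only: control vs HCIP |
|---|---|---|---|
| 10% | 3.25 | 1.3% | 10% vs 20% |
| 20% | 6.5 | 2.6% | 20% vs 40% |
| 30% | 9.75 | 3.9% | 30% vs 60% |

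The arms have the same severe risk, yet severity appears to double on HCIP.

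**Scenario B: plasma halves infection equally at every severity.** Severe risk per randomised participant is 0.13q vs 0.065q, which is 1.3% vs 0.65%, 2.6% vs 1.3% and 3.9% vs 1.95%. The infected-only contrast is q vs q. A real halving of severe disease does not show.

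**Scenario C: an intermediate case.** Give participants a normally distributed frailty that raises the log-odds of severity by 1 per standard deviation, and let plasma have no effect on severity given infection in anyone. Fix infection at 13% and 6.5% and q at 20%. Vary the frailty slope for infection in controls from 0 to 1, and the extra slope on HCIP (plasma working less well in the frail) from 0 to 1. The HCIP severe share among the infected then runs from 20.0% to 34.2% against 20% in controls. Severe risk per randomised participant falls from 2.6% to between 1.3% and 2.2%. The restricted contrast can look adverse while plasma reduces severe disease.

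**The case against.** The strongest reply is that the SAP has already moved on. It cites a list dated 5/29/2021, while the protocol is dated December 23, 2020, so 5.2.2 may be superseded wording. That is plausible, and it is why the repair is cheap. But the SAP text available here does not state that it replaces 5.2.2. A precedence note elsewhere in the SAP cannot be excluded.

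It is also fair that the loss of comparability is conditional. If plasma had no effect on infection, the infected subsets would be comparable in expectation. The trial is planned on the opposite expectation.

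The illustration rests on assumed severe shares and on symptomatic rates. Definitions of the endpoint vary: both symptoms and a positive RT-PCR in Protocol 5.2, either or both in Protocol section 1 and SAP Study Design, and a positive test with or without symptoms in SAP Primary Analysis. If asymptomatic infections count, the restricted set is larger, but the selection remains.

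Two stronger readings are tempting and are not supported:

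- **A false signal of antibody-mediated enhancement.** Harm is not monitored through 5.2.2. Protocol 8.3 follows the numbers of deaths and ARDS cases by arm, and 5.2.1 compares SAEs and Grade 3 or higher AEs between randomised arms by Fisher's exact test. Tables 2 and 4 of 8.3 do use symptomatic denominators, but the monitored quantity is the arm count, which is equal in scenario A. The restricted contrast is also sparse: 3/16 vs 3/32 gives a two-sided Fisher p of 0.39.
- **Invented events.** For participants who skip a level, the protocol says "we will interval censor the lower events between the two time points prior to more severe and time of severe clinical event". This bounds the time at which someone passed a lower threshold, which is coherent when each level means this severe or worse. No bias from it has been shown.

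One further objection shapes the fix. On the SAP scale about 90% of participants fall in level 7, since 1 − 0.0975 = 0.9025, so infection dominates the ordinal result. As an illustration using a Mann-Whitney win probability (not the SAP's estimator), with 1.3% severe in controls, the value is 0.533, 0.532 or 0.531 as HCIP severe risk is zero, unchanged or doubled. Event-specific incidence from randomisation says more about severity and should not be discarded.

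**Conclusion.** The point holds. Followed as written, 5.2.2 gives a severity contrast in a group selected by the outcome that plasma is meant to change. It also contradicts the protocol's own time origin, the endpoint in 5.3 and the SAP population.

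Under the planned rates and assumed severe shares of 10% to 30%, the contrast can show a doubling when severe risk is equal, or no difference when severe risk is halved. These are illustrations of what can happen, not forecasts. They depend on plasma affecting infection, on the assumed shares, and on symptomatic rates standing in for all infections.

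The consequence is confined to a secondary outcome. The primary analysis is unaffected. No defect in safety monitoring and none in the interval-censoring rule is claimed.

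**What to change.** 1. Delete the infected-only restriction from Protocol 5.2.2, and the words "after individuals develop SARS-CoV-2 infection" from the secondary objective in both section 1 and section 4.1.3.
2. Define the secondary severity comparison as one of all modified-ITT participants by randomised arm, and name the SAP ordinal analysis as the secondary analysis in both documents.
3. Keep the event-specific cumulative incidence from randomisation as a supporting analysis in the same unrestricted population, with each level defined as this severe or worse.
4. Use one severity scale throughout and reconcile it with the endpoint in 5.3, which counts death or mechanical ventilation, whereas level 2 of the scale also counts ICU care. The single scale should also place non-hospitalised participants who have symptoms but no positive test, because SAP levels 5 to 7 leave them without a category. The unfinished sensitivity-analysis sentence in SAP Secondary Analyses should be completed at the same time.
5. Report severity among infected participants descriptively, with no test between arms.

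The cost is wording in the two documents. No new data are needed, and the SAP already contains the unrestricted ordinal analysis.
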